There is currently limited information regarding the role of blood management in the benign gynecologic population and specifically, in patients who are scheduled to undergo surgery for fibroids and/or abnormal uterine bleeding. A thorough search through PubMed and clinicaltrials.gov did not reveal any studies on this issue. In 2019 at CCF only 2% of gyn patients at Main Campus were referred to blood management, but 12.6% of the main campus gyn population had a Hb of <10.0 g/dL. The overall goal of this study is to evaluate the role of preoperative blood management in optimizing surgical outcomes by reducing the co-morbidities associated with postoperative blood transfusion.

Specific Aims/Objective:

The primary objective of this study is to compare the change in baseline hemoglobin levels in patients in the study (Blood Management Protocol) and control ("usual care")

group who are undergoing hysterectomy for abnormal uterine bleeding. Change in baseline hemoglobin levels is defined as the difference of the hemoglobin level obtained within 72 hours prior to surgery and the hemoglobin level at 4 weeks postoperatively.

Our secondary objectives include 1. To evaluate the perioperative outcomes between the two groups including OR times, EBL, peri-operative transfusion rates, length of hospital stay, complications including intra-operative injuries, postoperative infection rates, readmission, and re-operation; 2. to assess patient satisfaction regarding their experience with the Blood Management protocol and extra outpatient infusion visits required using a patient questionnaire (PATSAT 35, Attached); and 3. to compare the quality of patient health and recovery between the two groups using the RAND-36 (Attached) assessment tool. The REDCap database will include potential identifiers to enable online surveys. The included potential patient identifiers include: date of birth, surgery date, and subject email (they provide for the study.)

Data variables that will be collected in the study are visible in the following table.

Patier	nt Demographics:
•	MRN
•	Age/ Date of Birth
•	BMI

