Race • Gravidity/Parity Prior abdominal surgery Prior cesarean section Diabetes Hypertension **Current Smoker** Former Smoker • Menopause status Type of surgery: Hysterectomy or myomectomy Type: Vaginal, laparoscopic, open, laparoscopic assisted vaginal hysterectomy, robotic • Surgery date, discharge date • Surgery date/ Discharge date • Subject email Primary objectives: • Change in hemoglobin levels o Baseline Hemoglobin (pre-op) o Post Op Hemoglobin level Secondary objectives: • Operative time Blood Loss • Perioperative transfusion rate • Length of hospital stay • Intraoperative Complications o Intraoperative injuries o Post-operative infection rates Readmission Reoperation • Patient Satisfaction • Quality of Health and Recovery • Number of infusions received • Days on PO iron therapy

Table 1.0 -- Data Collection Variables

We anticipate that patients undergoing blood management protocol will have a faster return to normal recovery and better quality of life scores during recovery using the RAND-36 assessment questionnaire compared to patients undergoing usual care. We also plan to evaluate additional cost of blood management treatments for oral iron, IV iron, and blood transfusion in regards to feasibility, and from a health care utilization standpoint.

Methods and Study Design:

This will be a prospective randomized control trial conducted in a single large-referral center where anemic patients undergoing hysterectomy for fibroids or abnormal uterine bleeding will be recruited and randomized to undergo Blood Management protocol or usual care.

Inclusion criteria are anemic patients (defined as Hgb ≤ 11g/dL within 30 days of initial MIGS consult visit), greater than 18 years of age, with abnormal uterine bleeding, or fibroids undergoing hysterectomy by laparoscopic, robotic, vaginal or open routes. Exclusion criteria are malignancy, pregnancy, sickle cell anemia or other blood dyscrasias, women who received blood transfusions in 30 days prior to surgery, women receiving EPO therapy, women who have undergone gastric bypass surgery, and women on therapeutic/full anticoagulation. Patients undergoing hysteroscopic myomectomy alone without will not be included in the study.

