Women meeting the above inclusion criteria who are undergoing elective surgery (hysterectomy) at the Cleveland Clinic Main Campus will be randomly allocated to receive presurgical optimization blood management referral versus usual care - defined as expectant management with no therapy, or PO iron therapy at the primary surgeon's discretion. Randomization following a computer generated number sequence and allocation will occur in person. Patients will be screened from multiple minimally invasive gynecologic providers with high volume surgical practices at a large teaching institution, and consented on their initial preoperative visit. (These MIGS surgeons are [name], [name], [name], [name].) Patients will be randomized to receiving a blood management referral or usual care. Patients will be randomized with permuted block randomization with block size 2 and stratified on care providers. Blood management work up protocol is visible in Table 1. Patients receiving usual care will receive anemia management provided by the primary physician that may include no treatment, continued observation, or oral iron recommendations in the pre-operative time.

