The intervention will include pre-surgical optimization blood management referral based on preoperative Hb levels ≤11.0. Currently it is not standard of care at the Cleveland Clinic to send all patients with Hb ≤11.0 due to secondary anemia to blood management. It is done currently at the provider/surgeons preference alone and not through a research protocol or guidelines. At the initial consultation visit a CBC will be drawn, patients will be given a consent form for the study and asked to review it. If a Hb ≤11.0 within 30 days of consultation visit is documented in EPIC, they will be consented and randomized at the consultation visit. All patients after initial consultation visit will be immediately sent to the lab for blood draw if they have not had Hb drawn within 30 days. Lab draw includes: CBC + differential, iron studies: iron, TIBC, ferritin, optional B12. If the initial consult visit occurs at Fairview or Hillcrest Hospital, the patient's follow up preoperative visit will be scheduled at the main campus where consent will be obtained. The blood management team then will receive the referral from primary surgeon's office via EPIC inbasket. Blood management coordinator will assess patient, arrange treatment, and orders will be cosigned by surgeon/referring provider. Blood management may further assess for symptoms of PICA, restless legs, and cold intolerance as symptomatic indicators of anemia. The Rand 36 study will be administered at either the consultation or the pre-operative visit. The PATSAT 35 will be administered at the postoperative visit only. Postoperative Hb levels will be collected by a CBC at the post-operative visit. All postoperative visits will be scheduled at the main campus. All surveys and consents will be obtained at visits that occur at the main campus.

[figure not shown]

Table 2: Blood Management Preoperative Iron Deficiency Algorithm

Blood loss intraoperatively will be measured as accurately as possible with suction device recording and quantitative blood loss and tapes/packs by weighing instead of only visual assessment.

[figure not shown]

Image: 1.0 -- Patient Flow Sheet

Justification for Sample Size:

Power Calculation:

Sample size was calculated to have 80% power to detect a difference between groups using a T-test at a significance level of 0.05. We assume that patients at 4 weeks will have a standard deviation in hemoglobin values of 1.2 g/dL (8) to detect a 1 g/dL difference between groups, we

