will need 48 patients total (24 per group) if the groups are of equal size. Assuming a 20% dropout rate, 60 patients total (30 per group) will be the target enrollment.

Cost and Payments to Subjects

The patients will have no additional costs due to participating in the study beyond the usual insurance copays and standard costs for appointments.

Quality Control Procedure:

Information will be provided to all department members involved in administration of the study. Follow up, data entry, and patient follow up will be closely followed by the research team (resident, fellow, staff physicians, MIGS NP's, Lead research nurse)

Process of Consent

Patients would be consented for participation in the study at their primary surgeon's office when shared decision making for proceeding with surgery is performed. Patients will receive no difference in care based on their participation in the study apart from the study protocol

Risks and Discomfort of the Project

The study has been designed to minimize as much risk as possible, and participants will be subjected to no more than minimal or standard risk for undergoing the intervention. Breach of confidentiality is a small risk. Physical risk are rare and unanticipated but would be limited to transfusion reaction to the IV iron therapy. There are no psychological risks for patients who participate in this study. Participants can also benefit from their participation in this study due to their altruistic motivation for partaking in research study they have contributed to scientific advancement.

Analysis plan

Approximately normally-distributed continuous measures will be summarized using means and standard deviations and will be compared using two-sample t-tests. Continuous measures that show departure from normality and ordinal measures will be summarized using medians and quartiles and will be compared using Wilcoxon rank sum tests. Categorical factors will be summarized using frequencies and percentages and will be compared using Pearson's chi-square tests or Fisher's Exact tests. All analyses will be done using SAS (version 9.4, The SAS Institute, Cary, NC) and a p < 0.05 will be considered statistically significant.

Timetable:

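### The sample size rests on the SD of a single 4-week hemoglobin, but the primary endpoint is a change from a pre-operative value taken after randomization, so 80% power is not established for the variable tested

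*Combined protocol and SAP*

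**What the plan says.** Under Specific Aims/Objective, the primary outcome is change in hemoglobin, defined as "the difference of the hemoglobin level obtained within 72 hours prior to surgery and the hemoglobin level at 4 weeks postoperatively". Table 1.0 also lists change in hemoglobin as primary.

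Under Justification for Sample Size, the calculation is for 80% power "using a T-test at a significance level of 0.05" to detect 1 g/dL between groups. Its variance input is: "We assume that patients at 4 weeks will have a standard deviation in hemoglobin values of 1.2 g/dL". The result is 24 per group (48 in total), raised to 60 for 20% dropout.

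On timing, Methods and Study Design says of eligible patients with a documented qualifying hemoglobin that "they will be consented and randomized at the consultation visit". The intervention then takes place before surgery.

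The Analysis plan has no rule specific to the primary endpoint. Approximately normal continuous measures "will be summarized using means and standard deviations and will be compared using two-sample t-tests", with a Wilcoxon rank sum test otherwise. No model adjusts for a baseline value or for surgeon, although the randomization is described as follows: "Patients will be randomized with permuted block randomization with block size 2 and stratified on care providers".

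**The concern.** The SD used for the sample size describes the spread of one measurement, whereas the endpoint is the difference between two measurements on the same patient. The spread of that difference depends on the pre-operative SD and on the correlation between the two values, and the protocol gives neither.

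The effect size has the same gap. The protocol does not say whether the 1 g/dL refers to the 4-week value or to the change. The value treated as baseline is drawn after randomization and after pre-operative treatment, so any benefit already present at that draw is subtracted from the endpoint.

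Only 48 evaluable patients are planned, and at 80.7% there is almost no margin. If the change score shows no difference, a reader cannot say whether the trial had a fair chance of detecting 1 g/dL.

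**Working it through.** **Inputs from the protocol.** Difference 1 g/dL, SD 1.2 g/dL, alpha 0.05, power 80%, 24 per group, 20% dropout. Sidedness is not stated. Two-sided is inferred because it reproduces 24 per group, while a one-sided test would need 18 (normal approximation).

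**Inputs that are assumptions.** The pre-operative SD (s0), the correlation between the pre-operative and 4-week values (r), and the share f of the treatment effect already present in the pre-operative value.

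**1. The plan's own figure.** A two-sample t-test (noncentral t) with standardized difference 1/1.2 = 0.833 needs 23.6, so 24 per group. Power at 24 per group is 0.807. Dropout: 48/0.80 = 60. The stated numbers reproduce for a single 4-week value.

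**2. Largest SD that keeps 80% power.** With 24 per group and a difference of 1 g/dL, the SD of the analysed variable may be at most 1.21.

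**3. SD of the change.**

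SD of change = sqrt(s0² + 1.2² − 2·r·s0·1.2) = sqrt(s0² + 1.44 − 2.4·r·s0)

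This is at most 1.2 only when s0² ≤ 2.4·r·s0, that is, when r ≥ s0/2.4. The correlation needed is 0.33, 0.42, 0.50 or 0.63 for s0 = 0.8, 1.0, 1.2 or 1.5.

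Example with s0 = 1.2 and r = 0.3: sqrt(1.44 + 1.44 − 0.864) = sqrt(2.016) = 1.42.

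**4. Power at 24 per group for a 1 g/dL difference in change** (SD of change in brackets):

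| s0 | r = 0 | r = 0.3 | r = 0.5 | r = 0.7 |
|---|---|---|---|---|
| 0.8 | 65% (1.44) | 79% (1.23) | 89% (1.06) | 98% (0.86) |
| 1.0 | 58% (1.56) | 73% (1.31) | 86% (1.11) | 97% (0.87) |
| 1.2 | 52% (1.70) | 67% (1.42) | 81% (1.20) | 95% (0.93) |
| 1.5 | 42% (1.92) | 56% (1.62) | 69% (1.37) | 88% (1.08) |

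In the row s0 = 1.2, the evaluable total needed for 80% power is 94, 66, 48 or 30, against the 48 planned.

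**5. Effect size.** If a share f of a 1 g/dL 4-week effect is already in the pre-operative value, the difference in change is 1 − f. With the SD of change held at 1.2:

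- f = 0: difference 1.00, power 81%
- f = 0.25: difference 0.75, power 56%
- f = 0.50: difference 0.50, power 29%

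**6. The alternative analysis.** Take ANCOVA of the 4-week value on pre-randomization hemoglobin and surgeon, with four surgeons as the protocol lists. Residual degrees of freedom are 48 − 1 (intercept) − 1 (treatment) − 1 (hemoglobin) − 3 (surgeon) = 42. Allowing for chance baseline imbalance, power is 79.6%, 83.6% or 87.6% if the covariates explain 0, 10% or 20% of the variance. Those shares are assumptions.

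**The case against.** - **The 1.2 may be an SD of change, loosely described.** It is cited to a systematic review that the Background describes as reporting varied changes in hemoglobin. The documents cannot exclude this. The text as written nevertheless says the SD is of values at 4 weeks. If an SD of change was meant, the protocol should say so, and the question about the effect size would remain.
- **The lowest powers need extreme inputs.** Zero correlation between two hemoglobin values in the same woman is a bound, not an expectation. With equal SDs and r = 0.5 the planned size holds exactly. This is fair: the table shows an undocumented input and is not evidence that the trial is underpowered.
- **A completed trial is read from its estimate and confidence interval.** This is also fair, and the t-test on change remains a valid test under randomization. The defect lies in the justification of the sample size and in what the endpoint measures.
- **Replacing the outcome goes further than supplying a missing SD.** An SD alone would not resolve the post-randomization baseline, which is the stronger reason for the change. ANCOVA's precision gain may be small, since eligibility at hemoglobin of 11 g/dL or below narrows the covariate's range. The proposal does not depend on that gain.
- **Ignoring the surgeon strata does not cause the mismatch.** Agreed: that omission tends only to make the test mildly conservative.

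**Conclusion.** The concern holds. The 80% figure is correct for 4-week hemoglobin with SD 1.2 and is not established for the stated primary endpoint. Over the assumed range (s0 from 0.8 to 1.5, r from 0 to 0.7), power on the change with a full 1 g/dL difference runs from 42% to 98%. It would be lower again if part of the effect is already present before surgery. The documents do not allow a single corrected figure and do not show which side of 80% the trial falls on. The gap should be closed before the sample size is relied on, although the planned test is not invalid.

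**What to change.** **Preferred.** Make 4-week hemoglobin the primary analysed outcome. Compare the groups by ANCOVA, with the pre-randomization hemoglobin (the eligibility or consultation value) and surgeon as covariates. Do not use the 72-hour value as a covariate, because treatment can alter it. Restate power as about 80% for 4-week hemoglobin with SD 1.2, higher only to the extent that the covariates explain variance.

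**If the change score is kept.** State its SD, or both SDs and the correlation, with a source. Show power over a plausible range, and justify why 1 g/dL applies to a change from a post-randomization pre-operative value.

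**Cost.** No extra patients or visits. The primary outcome in the aims is reworded. Two fields are added to Table 1.0, which now lists only the pre-operative baseline hemoglobin and no surgeon; both should be retrievable from the medical record or the randomization list. The covariates use about four degrees of freedom, so power stays near 80% with no reserve if they explain little. If ethics approval and registration are already in place, an amendment and a registry update are also needed.

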A Blood management protocol was recently developed at the Cleveland Clinic whereby either confirmed or suspected anemic patients with abnormal uterine bleeding scheduled for surgical management are referred to Blood Management for assessment of laboratory studies (CBC, Ferritin, iron, TIBC, %Sat) and a care plan is development. Several factors are considered in designing a treatment plan including current blood loss, anemia symptoms, scheduled or upcoming procedures, and others. Treatment plans may include observation alone or oral iron versus intravenous iron. Iron deficiency is calculated using the Ganzoni calculation for patients receiving intravenous iron. Per the Blood Management Protocol: An anemia screening lab panel will be ordered, in combination with a referral to the Blood Management clinic via WHI Blood Management Referral Smartset. This order set will automatically preselect the lab panel — complete blood count (CBC), iron, total iron binding capacity (TIBC) and ferritin — and the referral to the Blood Management clinic. The patient will automatically receive information in the after-visit summary regarding the Blood Management clinic referral. Any correctable causes of anemia will be addressed preoperatively by the Blood Management group. Measures used may include the use of intravenous iron or oral iron. See Algorithm in Table 2.0.

Using Ganzoni Formula Calculator: http://www.al-nasir.com/www/PharmCalc/mob exec calc.php?ID=ganzoni

Clinical data for calculator:

- a) Current hemoglobin
- b) Weight in kg
- c) Target hemoglobin (see table below)

Ganzoni Target Hemoglobin	Female
High Blood Loss* (> 3 gm/dL)	13 gm/dL

Low Blood Loss* (1-2 gm/dL)	12 gm/dL
Non-surgical*	12 gm/dL
Unknown*	12 gm/dL

*High blood loss defined as expected drop in hemoglobin > gm/dL postoperatively i.e. CABG, Valve, AAA, lower extremity joint replacement,multi-level spine w/instrumentation; Low blood loss expected drop hemoglobin 1-2 gm/dL i.e. hysterectomy, simple colectomy, laparoscopic or robotic assisted procedures; Non-surgical is medical iron deficiency treatment; Unknown are default targets.

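### Table 1.0 lists no iron-related adverse event, not even the reaction to IV iron that the protocol names as its one physical risk

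*Combined protocol and SAP*

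**What the plan says.** Risks and Discomfort of the Project names a single physical risk: "Physical risk are rare and unanticipated but would be limited to transfusion reaction to the IV iron therapy".

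Specific Aims/Objective introduces the dataset with "Data variables that will be collected in the study are visible in the following table", which points to Table 1.0. For iron treatment, that table lists "Number of infusions received • Days on PO iron therapy". Its harm-type outcomes read "Intraoperative Complications o Intraoperative injuries o Post-operative infection rates Readmission Reoperation", and it also has the perioperative transfusion rate. These match the first secondary objective, which compares the groups on perioperative outcomes, among them "complications including intra-operative injuries, postoperative infection rates, readmission, and re-operation".

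On treatment, the Background says of the Blood Management clinic: "Measures used may include the use of intravenous iron or oral iron". It also allows observation alone. Methods and Study Design describes usual care as "defined as expectant management with no therapy, or PO iron therapy at the primary surgeon's discretion". IV iron is therefore a listed option in one arm only.

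The Quality Control Procedure section mentions follow-up and data entry but not adverse-event recording. The Analysis plan gives generic tests by type of variable and no safety summary.

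**The concern.** The plan measures how much iron each patient receives and states what physical harm it might do, but does not list that harm as something to record. An event without a study variable is not systematically extracted, compared or reported, even if it is noted in the patient's chart.

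The gap lies in the treatment that randomization adds. Methods and Study Design says that sending every patient at or below the haemoglobin threshold to Blood Management is not current practice at the centre. Assignment to that arm can therefore create IV iron exposure that would not otherwise have occurred. If the trial shows a haemoglobin gain, a reader will ask how many patients reacted to an infusion and how many could not tolerate oral iron. The listed dataset could answer neither question.

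**Working it through.** **1. The named risk against the listed variables.**

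| Item | Listed in Table 1.0? |
|---|---|
| Number of infusions (exposure) | Yes |
| Days on oral iron (exposure) | Yes |
| Intraoperative complications and injuries | Yes |
| Postoperative infection | Yes |
| Readmission | Yes |
| Reoperation | Yes |
| Perioperative transfusion | Yes |
| Reaction to IV iron | No |
| Oral-iron intolerance | No |
| Adverse events in general | No |

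**2. Could a listed item capture the reaction?** The iron is given before surgery, as outpatient treatment when it is IV. A reaction at such a visit is not an operative injury, a postoperative infection, a readmission or a reoperation. PATSAT 35 covers patients' experience of the Blood Management protocol and the infusion visits, but it measures satisfaction and is given only at the postoperative visit. RAND-36 measures health and recovery. Neither is described as recording adverse events.

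**3. How many patients could be exposed?** Inputs from Justification for Sample Size: SD 1.2 g/dL, difference 1 g/dL, 80% power, alpha 0.05 (taken as two-sided). The exact two-sample t-test needs 23.6 per group, rounded up to 24, or 48 in total (power 80.7%). With 20% dropout, 48 / 0.80 = 60, or 30 per group. Both figures in the plan reproduce. The ceiling on IV-iron recipients is therefore about 30, one whole arm. The actual number is not given and is probably smaller, because observation and oral iron are also options. I use 30 (enrolled), 24 (evaluable) and 15 (an assumption: half the arm).

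**4. What could the count show if it were collected?** With zero events in n recipients, the upper limit of the two-sided exact 95% interval, which is the upper 97.5% bound, is 1 − 0.025^(1/n):

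- n = 30: 1 − 0.025^(1/30) = 11.6%
- n = 24: 1 − 0.025^(1/24) = 14.2%
- n = 15: 1 − 0.025^(1/15) = 21.8%

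The probability of seeing at least one reaction is 1 − (1 − p)^n. The documents give no reaction rate, so the values of p are assumptions:

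| Assumed true rate p | n = 30 | n = 15 |
|---|---|---|
| 0.5% | 14.0% | 7.2% |
| 1% | 26.0% | 14.0% |
| 2% | 45.5% | 26.1% |
| 5% | 78.5% | 53.7% |

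These figures describe the precision of a count that was collected. They do not measure the effect of leaving the field out. They show why the count should be reported with its interval, and why an absence of events should not be read as safety.

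**The case against.** The strongest reply is that the trial does collect harm data. Complications, infection, readmission, reoperation and transfusion are recorded in both groups and compared. Infection and readmission are not purely surgical and could in part reflect the intervention, and the word *including* in the secondary objective leaves the list of complications open. This stands against anyone who infers that the trial has no harm data or reports only benefit. It does not fill the gap: the objective concerns perioperative outcomes, and the table that carries it out adds no iron-related item.

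Second, not all of the material is visible. The iron-deficiency algorithm and the patient flow sheet are figures not shown, and the questionnaires are attachments not reproduced. Adverse-event recording there cannot be ruled out. This also stands, and it limits the point to the readable text, which does present Table 1.0 as the data to be collected.

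Third, a trial of this size says little about rare reactions. That is true, and the bounds above show it. It is a reason for modest reporting, not for leaving the count out.

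Fourth, a reader might infer from the term *transfusion reaction* that an iron reaction would be coded as a red-cell transfusion event. The documents do not show this. The same phrase names IV iron as the source, and Table 1.0 has a transfusion rate but no transfusion-reaction field. It is a wording slip.

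Fifth, the primary objective is change in haemoglobin, and nowhere does the protocol commit to recommending a change of practice. The stakes are therefore the completeness of the report, not the validity of the primary result.

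**Conclusion.** The point holds in a limited form. The readable protocol collects perioperative harm outcomes by arm but lists no iron-related adverse event, including the one physical risk it names. Followed as written, the treatment-related harms of the intervention could not be reported.

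This rests on two things: that Table 1.0 is the dataset, as the text presents it, and that the unseen figures and attachments hold no adverse-event form. The exposed group is at most about 30 patients and probably fewer. With zero reactions, the upper 97.5% bound would run from 11.6% (30 recipients) to 21.8% (15 recipients, assumed). The trial cannot establish the safety of IV iron with or without the change, but with it the trial could state what was seen and how little that excludes. It is a worthwhile and cheap improvement that leaves the primary comparison untouched.

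**What to change.** Add to Table 1.0, for both arms and up to the 4-week visit:

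- infusion reaction: yes/no, date, severity, and whether the infusion was stopped (a record of what happened, not a treatment rule);
- oral-iron intolerance: yes/no.

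In the Analysis plan, state that these will be reported descriptively as counts with exact 95% confidence intervals by assigned arm, and also among patients who received each treatment. Say that the second grouping is not randomized. State in advance that at most about 30 patients will receive IV iron, give the bound for zero events at the number actually treated, and say that the trial cannot establish safety. In the risk section, write *infusion reaction* in place of *transfusion reaction* as a tidying edit. If the figures or attachments already provide for adverse-event recording, refer to it from Table 1.0.

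The cost is a few REDCap fields, a little extra chart abstraction, and one question on oral-iron tolerance at the existing postoperative visit. The enrolment target stays at 60 and the primary analysis is unchanged.

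### Operative time, blood loss and hospital stay are compared by valid but unadjusted tests that pool all hysterectomy routes and ignore the provider strata; a prespecified model with provider and intended route would be more precise if either is prognostic.

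*Combined protocol and SAP*

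**What the plan says.** The inclusion criteria in Methods and Study Design admit women "undergoing hysterectomy by laparoscopic, robotic, vaginal or open routes". The same section randomizes in permuted blocks of two, stratified by provider; four surgeons are listed. Route is not a stratum.

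Secondary objective 1, under Specific Aims/Objective, covers perioperative outcomes "including OR times, EBL, peri-operative transfusion rates, length of hospital stay", among others. Table 1.0 collects route as "Type: Vaginal, laparoscopic, open, laparoscopic assisted vaginal hysterectomy, robotic". It does not say whether this is the intended route or the route performed.

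The Analysis plan sets the test for each continuous measure: "Approximately normally-distributed continuous measures will be summarized using means and standard deviations and will be compared using two-sample t-tests". Non-normal and ordinal measures get a Wilcoxon rank sum test, and categorical ones a chi-square or Fisher test. No covariate, stratified test, or sensitivity analysis by route or provider is named.

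**The concern.** Operative time, blood loss and stay can reasonably be expected to differ between open and other routes, and perhaps between surgeons. An unadjusted two-sample test leaves that variation in the error term, so the comparison is noisier than it need be. It also makes no use of the stratification built into the randomization.

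The second issue is interpretation. In a trial of this size the arms may differ by chance in their share of open cases. If so, the plan offers no prespecified analysis to show how much of an observed difference goes with route, and an adjustment added after seeing the imbalance would be post hoc.

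**Working it through.** **The plan's own figure.** Justification for Sample Size asks for "80% power to detect a difference between groups using a T-test at a significance level of 0.05", with a "standard deviation in hemoglobin values of 1.2 g/dL (8) to detect a 1 g/dL difference between groups". Taking the test as two-sided (the plan does not say), the normal approximation gives 2 × (1.960 + 0.842)² × 1.2² / 1² = 22.6, so 23 per arm. The exact noncentral t gives power of 78.9% at 23 per arm and 80.7% at 24. Thus 24 per arm reproduces, and 48 / 0.8 = 60 reproduces the enrolment target. These figures concern hemoglobin only; nothing is sized for the surgical outcomes.

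**Inputs that must be assumed.** Let p be the share of open cases and d the open versus non-open difference in within-route SDs. The documents give neither. I use p from 5% to 40% and d from 1 to 2. The low end of p matters because patients come from minimally invasive surgeons.

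**Precision.** Unadjusted variance relative to route-adjusted variance is 1 + p(1 − p)d². The reduction in standard error (SE) is 1 − 1/√ratio.
- Low end: 1 + 0.05 × 0.95 × 1² = 1.0475, a reduction of 2.3%.
- High end: 1 + 0.40 × 0.60 × 2² = 1.96, a reduction of 28.6%.

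**Chance imbalance.** The last two columns give the exact binomial probability that the arms differ by 20 points or more in open share, ignoring any balance from provider strata. That is a gap of at least 5 women at 24 per arm and at least 6 at 30 per arm.

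| Open share | SE cut, d = 1 | SE cut, d = 2 | Imbalance, 24 per arm | Imbalance, 30 per arm |
|---|---|---|---|---|
| 5% | 2.3% | 8.3% | 0.4% | 0.2% |
| 10% | 4.2% | 14.3% | 3.0% | 1.8% |
| 20% | 7.2% | 21.9% | 10.3% | 7.5% |
| 30% | 9.1% | 26.3% | 15.5% | 12.0% |
| 40% | 10.2% | 28.6% | 18.4% | 14.7% |

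A 20-point imbalance moves the unadjusted difference by 0.2d, which is 0.2 to 0.4 within-route SDs.

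**Simulation.** Settings: 24 per arm, blocks of two, 20% or 30% open, d of 1 to 2, and route unrelated to provider.
- With no treatment effect, the overall false-positive rate is 4.9% to 5.3% unadjusted and 4.8% to 5.3% adjusted.
- Among only those simulated trials with an imbalance of 20 points or more, it is about 9% to 21% unadjusted and about 5% adjusted.
- With a true effect of 0.8 within-route SD, power is 51% to 71% unadjusted and about 76% adjusted.

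**The case against.** The strongest reply is that randomization already makes the unadjusted tests valid: their p-values allow for chance imbalance in route. That stands. A reader might infer that the plan inflates the false-positive rate or biases these comparisons. It does neither. The 9% to 21% applies only given a realised imbalance and is not the error rate of the design.

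Four further objections also stand in part.
- **Size of the gain.** A reader might expect a large gain as a matter of course. The upper figure needs both 40% open cases and a 2 SD route effect. With minimally invasive surgeons, 5% to 10% open is plausible, and with a 1 SD effect the gain is then only 2% to 4%. Differences between intended and performed route would shrink it further.
- **Number analysable.** The plan's 24 per group is the evaluable number for 4-week hemoglobin: "Assuming a 20% dropout rate, 60 patients total (30 per group) will be the target enrollment". Surgical outcomes are known by discharge, so up to 30 per arm may contribute.
- **Timing of route.** It is tempting to say that route is settled at consent and that Table 1.0 holds the route performed. The documents state neither. They place consent at the visit where the decision to operate is shared with the patient.
- **Provider strata.** These balance route in part, to the extent that surgeons differ in the routes they use.

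Simple tests for secondary outcomes in a 60-patient trial are defensible. What the objection does not answer is the missing prespecified analysis, or the failure to use the randomization stratum.

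**Conclusion.** The point holds as one of efficiency and prespecification, not validity. The planned tests for operative time, blood loss and stay keep their nominal error rate, but they discard precision if route or provider is prognostic and leave no planned answer to a chance route imbalance.

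The standard error could fall by about 2% to 29%. This rests on assumed values of 5% to 40% open cases and a 1 to 2 SD route effect, and on a route term that captures the whole of that effect. The probability of an imbalance of 20 points or more ranges from about 0.2% to 18%, depending on open share and on whether 24 or 30 women per arm are analysed. The gain from adjusting for provider cannot be sized from the documents.

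A reader should not carry this over to the main result: the primary hemoglobin endpoint and the sample size are untouched. The change is worth making because it is cheap and has to be fixed before outcome data are seen.

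**What to change.** 1. Add one field, completed before allocation is revealed, for the intended route, with undecided as an option. State in advance how undecided is classed.
2. For log operative time and log blood loss, prespecify a linear model with arm, provider and intended route (open versus not open), reported as a ratio of geometric means with a 95% confidence interval.
3. For length of stay, replace the plain Wilcoxon test by a van Elteren test stratified on intended route.
4. Do not adjust for route as performed, since conversions and changes of plan arise after randomization.
5. Prespecify a rule for sparse data. At 5% to 10% open, only about 2 to 5 of 48 women would be open cases (48 × 0.05 = 2.4; 48 × 0.10 = 4.8). If planned open cases fall below a count set in advance, drop the route term or stratum, keep provider in the models, and stratify the van Elteren test on provider instead.

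The cost is the one pre-randomization field, a few lines of SAS, and about four model degrees of freedom: three for four surgeons and one for route. This is affordable with 48 to 60 women. Enrolment, treatment and the primary analysis do not change.
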